## Statistical Analysis Plan (SAP)

A decision to remove 1 or more treatment arms from the long-term extension study may occur as information from the parent study becomes available. Subjects already enrolled in the long-term extension study may be switched to selected dose regimens for continued evaluation at that time. This decision is anticipated to occur approximately 1 year after the start of the long-term study.

When all subjects have completed the PsA parent Phase 2 study, the blind will no longer need to be maintained for that cohort, and this long-term extension study will have the option to become open-label for those subjects. At that time, the dummy placebo administration will be removed. Note: the timing of switch to an open-label design may differ across the cohorts of subjects entered, dependent on the parent study. If other studies are also included in the long-term extension study, similar considerations for maintenance of blind will be necessary. Those subjects will be entered as separate cohorts and procedures such as continued double-dummy dosing regimens will be utilized, even after other parent Phase 2 cohorts have the option to switch to open-label.

In PsA Phase 2 study [CLR\_16\_23 PsA study], both tildrakizumab, 200 mg q12 weeks and tildrakizumab 100 mg, q12 weeks provided similar efficacies in the ACR20, ACR50, and ACR70 at Week 24. The lowest dose of 20 mg q12 weeks, did not demonstrate superiority over placebo in ACR70 and had numerically lowest ACR50 response rate among the active doses tested. The highest dose of tildrakizumab 200 mg q4 weeks, did not provide significant benefit over tildrakizumab 200 mg, q12 weeks. Therefore, the dose regimen of tildrakizumab 100 mg, q12 weeks is chosen for the long-term extension study going forward.

After all subjects switch to receive 100 mg tildrakizumab Q12W in an open-label fashion, there will be no efficacy assessments and the primary focus is the long-term safety of tildrakizumab.

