## Statistical Analysis Plan (SAP)

- 200 mg q12 weeks arm: subjects will receive tildrakizumab 200 mg (two 1-mL injections of 100 mg/mL) at Weeks 8, 20, 32, 44, 56, and all subsequent 12-weekly time points to Week 200, as well as placebo (two 1-mL injections) at interim 4-weekly time points commencing at Baseline of the Phase 2 parent study up to Week 196
- 100 mg q12 weeks arm: subjects will receive tildrakizumab 100 mg (one 1-mL injection of 100 mg/mL + 1 mL placebo) at Weeks 8, 20, 32, 44, 56, and all subsequent 12-weekly time points to Week 200, as well as placebo (two 1-mL injections) at interim 4-weekly time points commencing at Baseline of the Phase 2 parent study up to Week 196

If a subject misses a visit and/or a scheduled dose of IMP, the site must reschedule a visit to ensure the dose of IMP is taken as soon as possible within the visit window. If after 2 attempts to reschedule, the subject still is not able to take the dose, the Sponsor should be contacted to determine if the subject should be discontinued from the study.

Following the last subject's Week 52 visit or early termination prior to Week 52, all subjects will begin migrating to receive 100 mg tildrakizumab SC injection Q12 weeks in an open-label fashion.

A detailed description of procedures and assessments to be conducted during this study is summarized in the Schedule of Assessments in Table 1 below.

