## Statistical Analysis Plan (SAP)

---

Abbreviations: AE = adverse event; BL = Baseline; C-SSRS = Columbia-Suicide Severity Rating Scale; D = days; ECG = electrocardiogram; ESR = erythrocyte sedimentation rate; EoT = End of Treatment; FU = Follow-up; hsCRP = high sensitivity C-reactive protein; IMP = investigational medicinal product; M = months; PK = pharmacokinetic; PsA = psoriatic arthritis; W = weeks; Y = year(s).

- a Visits will be scheduled every 12 weeks in the first two years, followed by every 24 weeks in the last two years. Collection of AEs and concomitant medications, as well as any unscheduled safety assessment deemed appropriate in the opinion of the Investigator to ensure subject safety, will be performed at each visit. In addition, following completion and database lock of the parent PsA Phase 2 study, the long-term extension study will have the option to become open-label for these subjects.
- b The BL visit of the study Visit 1 (Week 0, Day 1) will be the same as Visit 16, Week 52 of parent PsA study (or later for subjects who entered the wash-out phase from the parent study due to the timing of study site activation of the long-term extension study).
- c Subjects who withdraw from IMP at any time will complete the EoT/FU assessments approximately 4 weeks after administration of the last dose of IMP.
- d To include body weight and height only. Other demographic data including date of birth, sex, and ethnicity will be obtained from the parent study.
- e Report all AEs, SAEs, and concomitant medications that occur after signing of the Informed Consent Form for the long-term study. Any occurring prior to signing the Informed Consent Form for the long-term study should be recorded under Medical/Medication history.
- f IMP administration will occur on Day 1 of Week 0; followed by subsequent dosing Q12 weeks.
- g Blood samples are to be collected (pre-dose where applicable), after ECG and vital sign measurements.
- h At visits where lipids are assessed, the blood samples are to be collected (pre-dose where applicable) after 12 hours fasting, following ECG and vital sign measurements.
- i Urine pregnancy tests will be performed by using a urine dip stick. ESR will be performed at the site using materials supplied by the central laboratory. hsCRP samples will be sent to the central lab and analyzed by central lab.
- j A final anti-drug antibodies sample needs to be collected after 20 weeks from last dose.

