### 8.5.2 Treatment Compliance

Study drug compliance will be calculated as:  $100 \times \text{total number of doses administered} / \text{total number of doses planned to be administered}$  during the study drug exposure period. If only one syringe among the two is administered at a visit, the number of dose will be counted as 0.5. If both syringes are administered at a visit, the number of dose will be counted as 1. The total number of doses planned will count Weeks 0, 4, 8, 12, 16, 20, 24, 28, 32, 36, 40, 44, 48, 52, and all subsequent 4-weekly time points to Week 200. If a subject discontinues treatment, the total number of doses will be counted from Week 0 until the last dose before discontinuation.

Study drug compliance will be summarized by treatment group by the number of subjects (n), mean, SD, median, min, and max. They will also be summarized in categories “ $<80\%$  compliant” and “ $\geq 80\%$  compliant” using frequency tables.

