# Statistical Analysis Plan (SAP)

regimen received at the end of the parent study. A decision to remove one or more treatment arms from the long-term extension study may occur as information from parent studies becomes available, and subjects in this extension study may be switched to selected dose regimens at that time. The subjects will be summarized based on the actual treatment received at the beginning of the extension study.

All analyses will be performed using ASaT population.

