## 8.7 Safety analyses

Safety analyses will be conducted on the ASaT population and will be performed for all safety variables specified below.

The subjects will be summarized based on the actual treatment received at the beginning of the extension study.

The safety analyses of changes from baseline to a specific time point in safety variables (e.g., laboratory parameters, vital signs, and ECG) will only include subjects from ASaT who have data available for both the baseline and the time point under consideration unless otherwise specified. Where relevant, temporal relationships to parent study baseline will be described.

No statistical tests will be performed.

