# Statistical Analysis Plan (SAP)

- TEAEs leading to study discontinuation
- Serious TEAEs
- TEAEs leading to death.

An overall summary for the categories above will be presented by treatment group and overall.

Due to the various durations of exposure to a treatment, the exposure-adjusted AE incidence rate (per 100 subject-years) will be summarized by treatment group. The incidence of AEs will be presented by system organ class and PT. In addition, all TEAEs will be summarized by SOC, PT and treatment group using frequency counts and percentages (i.e., number and percentage of subjects with an event).

Where a subject has the same adverse event, based on preferred terminology, reported multiple times in the study, the subject will only be counted once at the preferred terminology level in adverse event frequency tables.

Where a subject has multiple adverse events within the same system organ class in the study, the subject will only be counted once at the system organ class level in adverse event frequency tables.

When reporting adverse events by intensity, in addition to providing a summary table based on the event selection criteria detailed above, summary table will also be provided based on the most intense event - independent of relationship to study treatment.

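### After the switch to 12-weekly 100 mg dosing, SAP compliance still expects 4-weekly doses, and the 200 mg columns keep collecting 100 mg data

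*SAP*

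**What the plan says.** **Compliance.** SAP 8.5.2 defines compliance as doses given over doses planned. For the planned count it says "The total number of doses planned will count Weeks 0, 4, 8, 12, 16, 20, 24, 28, 32, 36, 40, 44, 48, 52". The list then carries on at the same interval until Week 200. It applies to every arm and has no rule for a change of regimen. One syringe of a two-syringe kit scores 0.5. Discontinuers are counted up to their last dose. Results are also tabulated below and at or above 80%.

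**The switch.** SAP 3.3 ties the change of regimen to the final subject reaching one year in the extension or leaving sooner: "Week 52 visit or early termination prior to Week 52, all subjects will begin migrating to receive 100 mg tildrakizumab SC injection Q12 weeks". SAP 3.1 says of the move to open label: "At that time, the dummy placebo administration will be removed". Footnote f to the second schedule in SAP Table 1 reads "IMP administration will occur on Day 1 of Week 0; followed by subsequent dosing Q12 weeks". The Protocol synopsis gives the 100 mg dose as a single 1-mL injection.

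**Grouping.** SAP 8.1 provides three table columns, one for each starting regimen. SAP 8.6 recognises that "subjects in this extension study may be switched to selected dose regimens at that time". SAP 8.7 then says "The subjects will be summarized based on the actual treatment received at the beginning of the extension study", and SAP 8.8.1 uses the same rule for PK. In SAP 8.7.1, "the exposure-adjusted AE incidence rate (per 100 subject-years) will be summarized by treatment group". Protocol 12.3.1 instead groups by treatment received at particular time points, where that applies, and Protocol 12.3.2 groups PK by treatment received at the visit. SAP Section 1 says the SAP overrides the protocol's statistical text and will identify substantial differences. SAP Section 10 declares none.

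**The concern.** The compliance rule describes a dosing scheme that the same SAP brings to an end. Once a subject moves to 12-weekly dosing, two of every three planned doses no longer exist, and a subject who takes everything offered is scored as missing them. The error affects all three arms. The more time a subject spends on open-label dosing, the lower the score.

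The grouping rule affects the primary objective, long-term safety. For subjects who began on 200 mg, AEs, subject-years and concentrations arising on 100 mg every 12 weeks are reported in a 200 mg column. The 200 mg exposure-adjusted rates then describe a mixture of regimens, with nothing in the table to say so.

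**Working it through.** The documents state no compliance figure to reproduce, so the check is a direct count of scheduled doses.

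**Inputs**
- Planned doses (SAP 8.5.2): Weeks 0, 4, ..., 200, which is 200/4 + 1 = 51.
- 12-weekly dosing weeks (SAP 3.3; Protocol 9.1.3.1.2): 8, 20, 32, ..., 200.
- Last 4-weekly visit, S: not given for any subject, so it is varied. The earliest value for a subject still on treatment at the trigger is about Week 52. Earlier entrants switch later on their own clock, because the trigger is the last subject's Week 52 visit.
- Assumption: one post-switch syringe counts as one dose.

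**Compliance of a fully adherent completer**

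Doses given = (S/4 + 1) + number of 12-weekly weeks after S, up to Week 200.

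| S | 4-weekly doses | 12-weekly doses | Given/planned | Compliance |
|---|---|---|---|---|
| 52 | 14 | 13 | 27/51 | 52.9% |
| 104 | 27 | 8 | 35/51 | 68.6% |
| 132 | 34 | 6 | 40/51 | 78.4% |
| 136 | 35 | 6 | 41/51 | 80.4% |

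Perfect adherence therefore reaches the 80% category only if S is Week 136 or later.

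**If the 0.5 rule is applied to the single post-switch syringe**
- S = 52: (14 + 0.5 × 13)/51 = 20.5/51 = 40.2%.
- S = 104: (27 + 0.5 × 8)/51 = 31/51 = 60.8%.
- The 80% cut is first reached at S = 152: (39 + 0.5 × 4)/51 = 41/51 = 80.4%.

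**Does the discontinuation rule repair it?** No. With S = 52 and a last dose at Week 104, doses given are 14 + 5 = 19 and doses planned are 104/4 + 1 = 27, so compliance is 19/27 = 70.4%.

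**With planned doses counted by the regimen in force**, S = 52 gives (14 + 13)/(14 + 13) = 27/27 = 100%. The result is 100% for any S.

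**Attribution for a 200 mg starter who completes to Week 200**
- First 100 mg dose at Week 56: (200 − 56)/200 = 72% of dosing weeks are on 100 mg.
- First 100 mg dose at Week 116: (200 − 116)/200 = 42%.
- Counting from the last 4-weekly visit instead gives (200 − 52)/200 = 74% and (200 − 104)/200 = 48%.

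For illustration, suppose everyone in the column follows the first pattern and event rates are constant within regimen. The 200 mg column then shows 0.28 × (200 mg rate) + 0.72 × (100 mg rate), so only 28% of any true difference between the regimens remains visible. Under the second pattern 58% remains. If the two rates are equal, nothing is distorted.

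**The case against.** Grouping by starting regimen is deliberate. SAP 8.6, 8.7 and 8.8.1 all state it, and 8.6 does so just after acknowledging switches. SAP Section 1 gives the SAP precedence, Protocol 12.3.1 is permissive, and no tests are planned. Laboratory, vital-sign and ECG summaries are by visit, and PK is by time, so early and late data are on separate rows. Pooling over time mainly affects the cumulative AE tables and the exposure-adjusted rates, and the SAP does not spell out how subject-years are computed. Compliance is not an endpoint, and no analysis set uses the 80% cut.

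Much of this stands. The starting-regimen view is legitimate and worth keeping, and the consequences are descriptive. It does not rescue SAP 8.5.2, where the explicit dose list contradicts the SAP's own dosing. Nor does it explain why Section 10 declares no change, when Protocol 12.3.2 is firm on treatment at the visit and SAP 6.1 says analysis follows treatment actually received.

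Several stronger inferences are tempting but unsupported:
- **No adherent completer could reach 80%.** That needs calendar dates for first entry, last entry and switching. The documents give only an approximate start, and subjects only begin to migrate at the trigger.
- **The exposure-duration categories in SAP 8.5.1 are misassigned.** That section states no grouping rule of its own and refers to randomized drug, so the contrast is not established.
- **Everyone took 100 mg from extension Week 0**, as Protocol 10.2.4 and the first flow-diagram note (repeated in SAP 3.1) could suggest. The SAP openly covers two protocol versions. The wording is mixed, but it does not prove a difference in conduct.

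**Conclusion.** The compliance rule is wrong as written. A fully adherent completer scores 52.9% if the last 4-weekly visit is Week 52 and 68.6% if it is Week 104, and falls in the below-80% category unless that visit is Week 136 or later. These figures count one post-switch syringe as one dose and are lower under the 0.5 rule. They are illustrations over assumed switch weeks, because actual switch dates are not in the documents.

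The grouping point holds in a narrower sense. A defensible descriptive choice is the only view planned for these tables, departs from Protocol 12.3.1 and 12.3.2, and is not declared. It places roughly 42% to 72% of a 200 mg completer's dosing weeks under the wrong regimen label for first 100 mg doses between Weeks 116 and 56. The overall AE column is unaffected. So is the Week 52 interim, because migration begins only after the event that triggers it. The harm is confined to later and final descriptive tables by treatment group and, for compliance, to every arm.

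**What to change.** 1. In SAP 8.5.2, count planned doses as the 4-weekly kit visits up to each subject's switch and the 12-weekly list afterwards. State that one post-switch syringe is one dose.
2. In SAP 8.7 and 8.8.1, present AE counts, subject-years and concentrations by regimen received at the time, alongside the starting-regimen tables.
3. List the grouping difference from Protocol 12.3.1 and 12.3.2 in SAP Section 10.

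The cost is SAP wording and some extra table programming before the final analysis. No visits, data or subjects are added: Protocol 12.3.1 already requires treatment at AE onset in the AE listing, and dosing is already recorded.

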### 3.3 Study treatments and assessments

The maximum study duration from Baseline assessment to end of study is 208 weeks.

All subjects eligible for study participation will enter the extension study and continue to receive one of the 3 treatments as in the parent study. Study drug will be supplied as [REDACTED] and a subject at a visit is expected to receive two syringes packed in a kit. Below are the details:

- 200 mg q4 weeks arm: subjects will receive tildrakizumab 200 mg (two 1-mL injections of 100 mg/mL) at Baseline, Weeks 4, 8, 12, 16, 20, 24, 28, 32, 36, 40, 44, 48, 52, and all subsequent 4-weekly time points up to Week 200

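### SAP 8.5.2 counts planned doses every 4 weeks to Week 200 although all subjects move to 12-weekly dosing, so fully adherent completers fall below 80% compliance

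*SAP*

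**What the plan says.** SAP 8.5.2 sets compliance at 100 times doses administered over doses planned, summarised by arm as a continuous variable and split at 80%. The planned doses are listed week by week at 4-week intervals, closing with "48, 52, and all subsequent 4-weekly time points to Week 200". Two further rules apply:

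- Part doses: "If only one syringe among the two is administered at a visit, the number of dose will be counted as 0.5". Two syringes count as 1.
- Early stopping: "If a subject discontinues treatment, the total number of doses will be counted from Week 0 until the last dose before discontinuation". This shortens the 4-weekly count but keeps its spacing.

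These rules fit the blinded design in SAP 3.3, where "a subject at a visit is expected to receive two syringes packed in a kit". There the 200 mg 4-weekly arm is dosed at Baseline, Week 4 "and all subsequent 4-weekly time points up to Week 200", and the 12-weekly arms receive placebo "at interim 4-weekly time points commencing at Baseline of the Phase 2 parent study up to Week 196".

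The SAP also describes a different second phase. SAP 3.3 says that after the last subject's Week 52 visit, or earlier termination, "all subjects will begin migrating to receive 100 mg tildrakizumab SC injection Q12 weeks in an open-label fashion". SAP 3.1 says of the move to open label: "At that time, the dummy placebo administration will be removed". The amended schedule in SAP Table 1 (footnote f) has 12-weekly dosing after Week 0. Protocol 9.1.3.1.2 lists 18 dosing weeks (0, 8, 20, then every 12 weeks to 200), and the protocol synopsis describes each dose as a single 1-mL injection. Protocol 12.2.1 requires compliance to be summarised.

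**The concern.** The denominator belongs to the blinded phase and the dosing after the switch does not. After a subject switches, the denominator grows by three doses every 12 weeks while the subject can receive only one. The score therefore falls with time spent on open-label dosing, however well the subject adheres. The 80% split then partly measures when a subject switched and how long the subject stayed, and adherent long-stayers can rank below non-adherent early stoppers.

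The half-dose rule adds an ambiguity. It is written for a two-syringe kit, and the SAP does not say how a complete one-injection visit is scored.

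SAP 8.5.1 measures exposure from first to last dose date and ignores interruptions. The compliance table is therefore the planned summary that shows whether doses were actually taken within that interval. In a study whose purpose is long-term safety, a misleading version would undercut the reading of the exposure data.

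**Working it through.** The documents state no total of planned doses and no compliance percentage, so there is no figure of the plan's own to reproduce.

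**Inputs**

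- Planned doses for a completer (SAP 8.5.2): Weeks 0, 4, ..., 200, so 200/4 + 1 = 51.
- Needed for the upper category: 0.80 × 51 = 40.8, so at least 41 counted doses.
- Blinded phase (SAP 3.1, 3.3): every arm is injected every 4 weeks, with active drug or placebo.
- Open-label phase: 12-weekly, one injection (SAP 3.3; SAP Table 1 as amended; protocol synopsis and 9.1.3.1.2).

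**Formula.** Let S be the week of the last 4-weekly dose. For a completer who misses nothing:

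compliance = [(S/4 + 1) + w × (number of 12-weekly visits after S, to Week 200)] / 51

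Two points are open, which gives four readings:

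- A: w = 1, protocol's listed weeks
- B: w = 0.5, protocol's listed weeks
- C: w = 1, visits at S+12, S+24, ...
- D: w = 0.5, visits at S+12, S+24, ...

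Example for S = 52. There are 52/4 + 1 = 14 four-weekly doses. Listed weeks after 52 run from 56 to 200, which is 13 visits. Reading A gives 14 + 13 = 27; B gives 14 + 6.5 = 20.5. With a restart at Week 64 there are 12 visits, so C gives 26 and D gives 20.

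| S (week) | A | B | C | D |
|---|---|---|---|---|
| 52 | 27/51 = 52.9% | 20.5/51 = 40.2% | 26/51 = 51.0% | 20/51 = 39.2% |
| 104 | 35/51 = 68.6% | 31/51 = 60.8% | 35/51 = 68.6% | 31/51 = 60.8% |
| 132 | 40/51 = 78.4% | 37/51 = 72.5% | 39/51 = 76.5% | 36.5/51 = 71.6% |
| 136 | 41/51 = 80.4% | 38/51 = 74.5% | 40/51 = 78.4% | 37.5/51 = 73.5% |
| 140 | 41/51 = 80.4% | 38.5/51 = 75.5% | 41/51 = 80.4% | 38.5/51 = 75.5% |
| 148 | 43/51 = 84.3% | 40.5/51 = 79.4% | 42/51 = 82.4% | 40/51 = 78.4% |
| 152 | 43/51 = 84.3% | 41/51 = 80.4% | 43/51 = 84.3% | 41/51 = 80.4% |

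The last failing week is 132 (A), 148 (B), 136 (C) and 148 (D). Every S from 0 to 132 fails under all four readings.

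**Adherent subjects who stop early, S = 52.** The denominator is the number of 4-weekly points from Week 0 to the last dose.

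| Last dose (week) | A | B |
|---|---|---|
| 68 | 16/18 = 88.9% | 15/18 = 83.3% |
| 80 | 17/21 = 81.0% | 15.5/21 = 73.8% |
| 92 | 18/24 = 75.0% | 16/24 = 66.7% |
| 188 | 26/48 = 54.2% | 20/48 = 41.7% |

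Adherence is perfect in every row, yet the score falls as the subject stays longer.

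**A non-adherent comparison.** A subject who stops at Week 52 after missing 2 of 14 doses scores 12/14 = 85.7%, against at most 52.9% for a perfect completer with S = 52.

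**Denominator under the regimen in force, open-label visit = 1, listed weeks.** Adherent completers with S = 52, 104 and 132 score 27/27, 35/35 and 40/40, which is 100% each.

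**The case against.** The strongest point is consequence. This is one descriptive table. The only analysis set is defined by entry and at least one dose, no statistical tests are planned, and adverse event rates do not use the compliance score. The planned interim analysis has the same trigger as the migration, so it largely escapes. All of that stands and limits the severity. It does not make the table right.

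The formula in SAP 8.5.2 also speaks of doses planned within the exposure period, and a withdrawn dummy injection is arguably no longer planned. But a completer's exposure runs to Week 200, and the SAP then lists the 4-weekly weeks explicitly. A programmer would follow the list.

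Readings B and D can fairly be called strained, because the half-dose rule refers to one syringe of two and may not reach a one-injection visit at all. That is a reasonable reading. The Week 132 limit comes from reading A, which is the kindest to the plan, so nothing rests on B or D.

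SAP 8.9 allows a separate document for later interim analyses where methods differ. That route does not cover the final analysis. SAP section 1 requires deviations to be described in the study report, which would disclose a departure but does not correct the rule. Finally, SAP section 10 declares no change from the protocol, but this proves little because the protocol gives no compliance formula.

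**Conclusion.** The concern holds. Followed as written, SAP 8.5.2 produces a wrong compliance summary once subjects have switched. A completer who misses nothing and whose last 4-weekly dose is at or before Week 132 falls in the below-80% category under every reading considered. With a last 4-weekly dose at Week 52 the score is 39.2% to 52.9%.

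The result assumes full adherence, 4-weekly dosing up to S and 12-weekly dosing after it. The documents give no actual switch weeks, so the share of subjects affected is unknown. As a rough guide only: the protocol plans a start in about June 2018 and the amended version is dated 22 July 2020. A subject entering between 1 and 30 June 2018 would have been at about Week 108 to 112 on that date, and an entrant on 1 June 2018 would reach Week 132 on about 11 December 2020. If switches were made before then, all or nearly all completers would be affected.

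The effect is limited to the compliance summary and its 80% split in analyses after the switch. Exposure duration, the analysis population and the safety endpoints are untouched. It should be fixed before those analyses are run.

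**What to change.** Rewrite the planned-dose rule in SAP 8.5.2:

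1. Planned doses are the subject's scheduled dosing visits under the regimen in force: 4-weekly visits to the last blinded visit, then the scheduled 12-weekly visits, ending at the last dose before discontinuation or at Week 200.
2. State whether the 12-weekly visits are taken from the listed protocol weeks or counted from the switch, so that the denominator is unique.
3. State that a complete one-injection open-label visit counts as 1 dose, and restrict the half-dose rule to two-syringe visits.
4. Preferably report compliance for the blinded period, the open-label period and overall.

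The arm descriptions in SAP 3.3, which run 4-weekly to Week 196 or 200, should be reconciled with the migration text and the amended schedule.

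A separate matter, not needed for this correction, is when the blinded regimens end. Protocol 9.1.1 refers to Week 52 of the parent study, while SAP 3.1 and 3.2.2 refer to 52 weeks in the extension. These passages must be reconciled.

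The cost is SAP wording, a switch date per subject in the derivation, and a programming change. No new data are collected.

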#### 3.2.2 Blinding

The parent Phase 2 studies will retain a blind status at the time of the initiation of the extension study. When all subjects have completed the PsA parent Phase 2 study, this long-term extension study will have the option to become open-label for those subjects. Open label dosing will proceed only after all subjects have completed at least 52 weeks of blinded dosing in the long-term extension study. If other studies are also included in the long-term extension study, similar considerations for maintenance of blind will be necessary. Those subjects will be entered as separate cohorts and procedures such as continued double-dummy dosing regimens will be utilized, even after other parent Phase 2 cohorts have the option to switch to open-label.

PK and anti-drug antibodies (ADA) data will be kept confidential before unblinding.

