## 8.5 Extent of exposure

### 8.5.1 Treatment Duration

Duration of study drug exposure (in days) will be calculated as: last dose date – first dose date + 1 day, regardless of study drug interruption.

Study drug exposure will be summarised by treatment group using descriptive statistics.

Exposure to randomized study drug will also be categorised in intervals  $\leq 3$  months ( $<91$  days), 3-6 months (91-180 days), 6-12 months (181-365 days), 1-2 years (366-730 days), 2-3 years (731-1095 days),  $>3$  years ( $>1095$  days) and summarized by treatment group.

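### SAP 8.5.2 counts planned doses every 4 weeks to Week 200 although all subjects move to 12-weekly dosing, so completers who miss nothing fall in the <80% compliance category for any switch before Week 140

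*SAP*

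**What the plan says.** SAP 8.5.2 defines compliance as 100 times doses administered over doses planned during the exposure period. It lists the planned doses week by week, every 4 weeks from Week 0 to Week 52, "and all subsequent 4-weekly time points to Week 200". The only stated shortening is for early stoppers: "If a subject discontinues treatment, the total number of doses will be counted from Week 0 until the last dose before discontinuation". Credit is per syringe: "If only one syringe among the two is administered at a visit, the number of dose will be counted as 0.5", and a visit with both syringes counts as 1. The result is summarised by treatment group as a continuous variable and as below 80% versus 80% or more.

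SAP 8.5.1 sets the exposure period by dates: "Duration of study drug exposure (in days) will be calculated as: last dose date" minus first dose date plus one day.

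The dosing sections of the SAP describe two phases:

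- **Blinded phase.** SAP 3.1 has every subject attend dosing visits every 4 weeks for active drug or dummy placebo. SAP 3.2.2 adds: "Open label dosing will proceed only after all subjects have completed at least 52 weeks of blinded dosing in the long-term extension study".
- **Open-label phase.** After the last subject's Week 52 visit (or earlier termination), SAP 3.3 says "all subjects will begin migrating to receive 100 mg tildrakizumab SC injection Q12 weeks in an open-label fashion". On the dummy placebo, SAP 3.1 says "At that time, the dummy placebo administration will be removed". Footnote f of the amended schedule in SAP Table 1 reads "IMP administration will occur on Day 1 of Week 0; followed by subsequent dosing Q12 weeks".

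**The concern.** The planned-dose list describes only the blinded phase. Once a subject is on 12-weekly open-label dosing, each 12-week interval contains one real dose but adds three to the denominator. A subject who takes every scheduled dose therefore scores below 100%, and by how much depends on the week of the switch, which in turn depends on when the subject enrolled.

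This is not a matter of the SAP predating the change. SAP 1 cites the amendment of 22 July 2020, and SAP Table 1 reproduces the amended schedule. The list would be wrong even under the schedule in force before the amendment: footnote a of that schedule keeps the interim dosing visits, once open-label, only for subjects on a 4-weekly regimen, so the two 12-weekly arms would already have left the 4-weekly grid.

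At stake is a table in a long-term safety report that could show fully adherent subjects as poorly compliant and so misdescribe how reliably the drug was given.

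**Working it through.** The documents state no compliance figure, so there is none to reproduce. The check is a direct count.

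**Inputs**
- Planned doses as written (SAP 8.5.2): Weeks 0, 4, ..., 200.
- Blinded dosing visits: every 4 weeks (SAP 3.1, 3.3).
- Open-label dosing visits: every 12 weeks, last dose at Week 200, on the grid 8, 20, 32, 44, 56, ..., 200 (SAP Table 1, amended schedule; Protocol 9.1.3.1.2).
- Category cut-off: 80% (SAP 8.5.2).

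**Assumptions**
- S is the week of the first open-label dose and falls on the 12-weekly grid. No document gives a subject's switch week, so a range is shown.
- A complete open-label visit, which is one syringe (Protocol 4, test product), counts as one dose.

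**Completer with no missed dose**
- Planned as written = 200/4 + 1 = 51.
- Given = blinded S/4 (Weeks 0 to S − 4) plus open-label (200 − S)/12 + 1.

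| Switch week S | Blinded | Open-label | Given | Score as written |
|---|---|---|---|---|
| 56 | 14 | 13 | 27 | 27/51 = 52.9% |
| 80 | 20 | 11 | 31 | 31/51 = 60.8% |
| 104 | 26 | 9 | 35 | 35/51 = 68.6% |
| 116 | 29 | 8 | 37 | 37/51 = 72.5% |
| 128 | 32 | 7 | 39 | 39/51 = 76.5% |
| 140 | 35 | 6 | 41 | 41/51 = 80.4% |

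Week 56 is the earliest case and fits only the last entrants, because earlier entrants wait until the last subject has reached Week 52. The score first passes 80% with a switch at Week 140.

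**Discontinuer with no missed dose, last dose at Week L**
- Planned as written = L/4 + 1. Given = S/4 + (L − S)/12 + 1.
- S = 56, L = 80: 17/21 = 81.0%.
- S = 56, L = 104: 19/27 = 70.4%.
- S = 104, L = 152: 31/39 = 79.5%.

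Subjects who stop soon after the switch can stay above 80%; those who continue longer fall below it.

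**Interim after the last subject's Week 52 visit**
- A subject at Week 52 has 52/4 + 1 = 14 doses given and, within the exposure period to date, 14 planned: 14/14 = 100%. The rule works there.

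**Where the switch probably falls (inference only)**
- The planned start is about June 2018 (Protocol 4). Counting from 1 June 2018, the amendment of 22 July 2020 is about 112 weeks later. One year after the parent study's lock date of 05 Nov 2019 (Protocol 7.1) is about 127 weeks later. Both fall short of Week 140 even for the earliest entrant.

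**The case against.** The best defence is that the formula refers to doses planned during the exposure period. After the switch, 4-weekly doses are no longer planned, so a sensible programmer would count the regimen in force. That is how the rule ought to work, but it is not what the section goes on to say. The next sentences define the planned count by an explicit list of weeks, and SAP 8.5.1 makes the exposure period a span of dates. For a completer that span is Weeks 0 to 200 and contains all 51 listed points. The phrase limits the window and leaves the dosing frequency as listed.

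Other documents might repair the rule. SAP 8.9 allows a separate document for later interim analyses, SAP 9 places table templates elsewhere, and SAP 1 says deviations will be described in the study report. None of these supplies another rule for the final tables, and SAP 10 lists no changes. They do mean that the percentages above show what the written rule yields, and the reported table could differ if someone departs from it.

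The percentages also depend on an assumed switch week. That stands, and is why a range is given. Some text (Protocol 10.2.4, and note 1 to the study design figure in both documents) instead describes 100 mg every 12 weeks from extension Week 0. That reading makes the error larger: 18 doses given out of 51 is 35.3%.

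The half-dose rule is a side issue. It speaks of one syringe out of two, so it does not on its face apply to a one-syringe visit, and full credit is the natural reading. The gap deserves a clarifying sentence but is not part of the main error.

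Finally, the consequence is small, and that is accepted. Exposure duration uses dose dates, and a table with most completers below 80% would be noticed.

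**Conclusion.** The rule is wrong as written. Followed literally, it puts every completer who misses nothing into the below-80% category for any switch before Week 140, with scores from 52.9% (Week 56) to 76.5% (Week 128). It also pulls down discontinuers who continue for some time after the switch.

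This rests on a first open-label dose that falls on the 12-weekly grid and on full credit for a one-syringe visit. The wording and the counts are certain; the actual switch weeks are not known from the documents.

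The weight is minor. The error is confined to a descriptive table, mainly in the final report. The interim after the last subject's Week 52 visit is unaffected provided the count stops at the exposure period to date. The section shortens the count explicitly only for discontinuers, so that limit should be written down.

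**What to change.** In SAP 8.5.2, replace the fixed week list. Count planned doses every 4 weeks before, and every 12 weeks from, each subject's own switch date, up to the last dose, the data cut-off or Week 200, whichever comes first. With a one-syringe open-label visit counted as one dose, full adherence then scores 27/27 = 100% for a Week 56 switch and 35/35 = 100% for a Week 104 switch.

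Add one clarifying sentence: each visit is scored as syringes given divided by syringes planned under the regimen then in force, two in the blinded phase and one open-label.

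The cost is one corrected sentence, one added sentence and a per-subject switch date in the compliance program. No new data are needed.
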